Biochemistry. Recent studies in the [name] Laboratory have generated exciting preliminary results showing essential amino acid (EAA) supplementation attenuates quadriceps atrophy and accelerates the return of functional mobility following TKA (37). For patients on EAA, quadriceps atrophy was only -6% & -3% in the operative and non-operative quadriceps, respectively, six weeks after TKA but -18% & -10%, respectively, in patients on Placebo (a 3-fold difference). Of clinical relevance, these patients on EAA were able to maintain strength and demonstrated an accelerated return of functional mobility vs. Placebo, 6 wk post-TKA. At the cellular level, our preliminary results show that EAA supplementation

down-regulated catabolic signaling (FoxO3a) and up-regulated amino acid transporter (SLC36A2), regulated in development and DNA damage response (REDD1) and activating transcription factor 4 (ATF4) expression vs. Placebo. While studies by others have linked these molecules with the insulin like growth factor (IGF-I) and vascular endothelial growth factor (VEGF) (i.e., angiogenesis) pathways, whether they are directly stimulated by EAA supplementation in a clinical population remains unknown. We interpret these positive changes at the cellular level to be responsible for the reduction in muscle loss and, preservation of strength, and explain the acceleration of the return of functional mobility.

Our preliminary fractional synthesis data (FSR) show that older adults respond appropriately to acute ingestion of 20 g of EAA (i.e., similar response to young healthy controls). We also have preliminary FSR data showing that basal rates of muscle protein synthesis are similar between TKA patients ($0.0563 \pm 0.008\%$ /hour) and older healthy control subjects ($0.0566 \pm 0.008\%$ /hour). What is not known is what effect TKA has on muscle protein synthesis and breakdown in response to chronic EAA supplementation (for 1 week prior to, and for 6 weeks post-TKA). We have extensive experience with stable isotope tracer methods to determine fractional synthesis rates (FSR), a direct measure of muscle protein synthesis (31-35, 39-41, 50, 113, 114). However, in order to determine mechanisms, and link cellular changes in anabolic and catabolic pathways with atrophy (Placebo) and atrophy prevention (EAA) we must also quantify muscle protein breakdown.

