Our preliminary results show that EAA phosphorylates (inactivates) a primary regulator of muscle protein catabolism (FoxO3a). As well, EAA supplementation stimulated the expression of the anabolic amino acid transporter, which has gained attention due to its ability to act as both a transporter and signaling protein linked to the IGF-I signaling pathway (54, 102). Interestingly, we also measured an up-regulation of the transcription factor ATF4, which has been shown to stimulate the expression of amino acid transporters and promote protein anabolism (76). In vivo and in vitro experiments have shown that IGF-I treatment increased REDD1 expression in muscle (49), and recent studies have shown that REDD1 confers cyto-protective effects by mitigating cell stress (22, 120). REDD1 is upregulated by ATF4 (49, 76, 122). ATF4 is increased in the presence of insulin (4) and IGF-I (49), and plays an important role in mediating the effects of VEGF on cell growth and survival (3, 75, 93). Thus, ATF4 may be necessary for amino acid and protein anabolism (4). We have preliminary data showing that REDD1 expression is elevated with EAA. This is important because our preliminary results support mechanisms of action by which EAA up-regulate amino acid transporters via ATF4 that have implications for muscle protein metabolism (76). We interpret these results as supporting a mechanistic role in atrophy prevention.

Physiology. Immobilization following orthopedic surgery accelerates sarcopenia (99). For example, 1%/year = normal sarcopenia progression, but in our TKA patients, sarcopenia was accelerated by +18 and +10 years, in the operative and non-operative leg, respectively. However, in patients randomized to EAA, progression was only +6 and +3 years, respectively. Thus, EAA have the potential to mitigate early onset of sarcopenia. Preventing muscle atrophy bilaterally is clinically important, as early post-operative quadriceps weakness in the non-operative leg is directly linked to poorer long-term functional outcomes (126).

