Prospective, randomized, blinded, controlled, two-arm, parallel clinical trial design with 1:1 allocation ratio to EAA versus Placebo. Staged enrollment is planned; we will complete Aim #1 before enrolling into Aim #2.

Investigational Supplement.

This trial is being conducted under IND#121601, with mandates to report results from Aim #1 to the Food and Drug Administration (FDA). The investigational supplement (or Placebo) will be ingested twice-daily, at 10:00a and 2:00p for one week prior to TKA surgery.

- Aim 1 -Supplement will be compounded by Northwest Compounds, and ordered per standard of care for pharmaceutical ordering (fax or phone call) and dispensing.
- Aim 2 – Supplement will be supplied by MEND Nutrition, Inc. Supplement will come individual containers shipped directly to the [name] Lab. Containers will be distributed to patients by study coordinators. Patient will measure two (2) scoops per dose (twice daily). Scoop provided in each container.

Aim 1 Supplement will be suspended on the day of surgery and resume on post-operative day #1. On post-operative days where subject participates in physical therapy, supplementation will occur within one hour of treatment (20 g of EAA or Placebo). The EAA supplement or Placebo composition is described in Table 1 below. Our preliminary study suggest the EAA supplementation is safe and no subjects withdrew due to problems with supplement ingestion (37).

Aim 2 Supplement will be suspended on the day of surgery and resume on post-operative day #1. On post-operative days where subject participates in physical therapy, supplementation will occur within one hour of treatment (23.42 g of EAA or Placebo). The EAA supplement or Placebo composition provided by MEND Nutrition, Inc. is described in Table 2 below. Our preliminary study suggest the EAA supplementation is safe and no subjects withdrew due to problems with supplement ingestion (37). Supplement composition has changed due to new manufacturer/supplier of the supplement (MEND). To our knowledge there are no scientific or risk implications related to the change in proportions.

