Measures include structural (CSA of cell and extracellular matrix) and functional (mitochondrial respiration & inflammatory cell infiltration) determination. Muscle cell structure (CSA) and function (mitochondrial respiration) will be determined based on percent change from baseline and made relative to the non-operative leg (internal control). From muscle biopsies we will also isolate primary muscle cells (i.e., satellite cells).

To perform the biopsies, a small incision about the size of this dash “---” approximately at mid-thigh, through which a needle about the size of this letter “O” will be advanced into the muscle and fat. A piece of tissue will then be removed. This will be done on each leg.

The postoperative biopsies will be performed by the Principal Investigator ([name]). [name] has performed over 500 biopsies and he has performed over 200 tracer studies. The biopsies will be performed in his lab at the Center for Medical Education and Research, or at the Slocum Center, in the morning in a fasted state. This procedure involves the taking of a small piece of tissue from the leg, containing both fat and muscle. The skin is cleaned and made sterile, and the skin and tissue below are injected with local anesthetic, lidocaine (numbing medicine), to eliminate pain. Afterwards, the skin will be closed with a single stitch (Aim 1 only). The stitch will be removed at the lab in about 7 days (plus or minus one day to accommodate participant schedule).

During the surgery, the surgeon or one of his assistants will perform the biopsies. The patient will still be under anesthesia. The intraoperative biopsies will not have a stitch that requires removal. The site will be covered with a sterile dressing.

Primary cell isolation. Primary cells isolation studies will be performed using standard methods that exist in our lab in order to conduct experiments on muscle cells that could not be performed on subjects
UO IRB Protocol #12272013.024 PeaceHealth Protocol #551187

January 2019

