Gene Expression: RNA will be extracted from 15-20 mg of muscle tissue according to protocol (Molecular Research Center, Inc, Cincinnati, OH). High quality RNA will be determined using lab-on-chip microfluidic technology automated nucleic acid electrophoresis and analysis. Total RNA will be reverse transcribed into cDNA using the iScript cDNA Synthesis Kit (Bio Rad, Hercules, CA) on a C1000 Thermal Cycler (Bio Rad, Hercules, CA). Determination of relative mRNA expression will be performed using a CFX96 Real-Time System coupled to a C1000 Thermal Cycler (Bio Rad, Hercules, CA) and Genomics Core facility NextSeq 500 at the University of Oregon.

Mitochondrial respiration. Oxidative phosphorylation rates in response to 50 μ M ADP will be determined in saponin permeabilized vastus lateralis biopsies (5-10 mg) using the two-channel high resolution respirometer (Oroboros Oxygraph; Innsbruck, Austria) with the saturating concentrations of the following substrate combinations [in mM]: pyruvate [5] + malate [5], palmitoylcarnitine [0.04] + malate [5], succinate [10] + 100 nM rotenone, or malate [5] + glutamate [10]. Respiration studies were performed at an initial oxygen concentration of 300 μ M at 37°C in MiR06 respiration buffer containing [in mM] EGTA [0.5], MgCl₂·6 H₂O [3], K-lactobionate [60], taurine [20], KH₂PO₄ [10], HEPES [20], sucrose [110], 1g/L BSA, 280U/ml catalase, pH 7.4 [with KOH].

Mitochondrial dysfunction may introduce sample bias as well as negatively impact short and longer-term function. To account for this, we propose to measure mitochondrial respiration using the Oroboros O2k respirometer, and normalize results statistically and use the non-operative leg as internal control.

Secondary Outcome Measures. Study Aim #1 will allow the team to collect preliminary functional outcome data to better inform the long-term study (Aim #2). The secondary outcome measures will be quantified using the following study activities and procedures:

- **Muscle volume.** The MRI unit is located at the Lewis Center for Neuroimaging (LCNI) on the University of Oregon campus. Should the MRI unit at LCNI be unavailable within study-specific assessment points (i.e. scheduling or mechanical issues), the MRI at the Slocum Center for Orthopedics will be utilized. In addition, patients in partnership with the study team, may elect to have all scans performed at the Slocum Center.

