Power analyses. For our power calculations, we have assumed a Type I error rate (α) of $.05$, two-tailed. We based power calculations on effect sizes (d) that we derived from analysis of preliminary data preliminary data and prior studies (10, 30, 32, 33, 36, 41, 51, 113). We calculated d as the standardized mean difference between treatment conditions at follow-up: $d = (x_C - x_T)/S$, where x_C represents the primary outcome mean in the Placebo and EAA conditions and S is the pooled standard deviation, after adjusting x for pretest scores and covariates (sex, tourniquet time, age, body mass index, fat/carbohydrate/protein intake).

We propose to enroll **40 total subjects for Aim 1** who are retained through protocol completion (20/group, EAA and Placebo, randomized to either 1 week or 2 week post-operative biopsies), and **80 total subjects** (40/group, EAA and Placebo) **for Aim 2** who are retained through protocol completion to account for possible attrition and to ensure sufficient power to test the hypotheses that EAA therapy up-regulates basal levels of muscle protein synthesis, and reduces post-operative atrophy bilaterally, preserves quadriceps strength, and improves functional mobility relative to a Placebo condition.

Effect sizes. Effect sizes were as follows: (a) Cell and FSR data: REDD1 $d = 1.24$, SLC36A2 $d = 1.27$, and FSR $d = 1.51$ (FSR calculated from mean change from baseline). The mean effect across outcomes was $d = 1.37$, reflecting large effects. (b) Physiological and functional data (percent change from Baseline to 6 wk): operative quadriceps volume $d = 1.52$, and isometric strength $d = .90$; non-operative quadriceps volume $d = 1.05$, and isometric strength $d = .66$; timed up-and-go test $d = 1.03$, timed stair ascent $d = 1.08$, timed stair descent $d = 1.13$, and six-minute walk test $d = .70$. Mean effect size was $d = 1.01$, reflecting large effects.

Power calculations. Power calculations were based on the sample size and minimally detectable ES (MDES) as follows:

- **Aim #1:** For a sample size of 20 completed subjects/group (10/group for metabolic studies, however, EAA vs. Placebo = 20 total EAA and 20 total Placebo). Aim 1, proposed study can detect

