and attrition when conducting a clinical trial. Our subjects are older adults who are undergoing a major operation. However, our preliminary studies are evidence that we are very experienced with this patient population. The average number of TKA patients who complete our studies is 3-5/mo. We are therefore very confident that we will be able to complete studies on 40 TKA patients (Aim 1) and 80 TKA patients (Aim 2); 120 over the entire 5 year study. Issues that present potentially unique problems to our longer-term study are addressed below.

Statins. A potential limitation with long-term muscle cell function of our clinical study is concurrent use of statins, which have a strong potential to compromise muscle mitochondrial function (7, 68, 109, 117). Over 50% of our TKA subjects use statins. Mitochondrial dysfunction may introduce sample bias as well as negatively impact short and longer-term function. To account for this, we propose to measure mitochondrial respiration using the Orophorus O2k respirometer, and normalize results statistically and use the non-operative leg as internal control. Thus, measuring mitochondrial respiration will allow us to determine the effects of muscle preservation and accelerated recovery of functional mobility (EAA) while accounting for statin use between groups as well as between sex and over time statistically.

Research Population & Recruitment Methods

Study populations for Aim #1 and Aim #2 are identical. In addition, the recruitment process does not differ between the short-term, biochemistry study (Aim #1) and the longer term, physiologic study (Aim #2).

Target Population.

Both aims will target older adults, ages 50 – 80 years (Aim 1) and 40 – 80 years (Aim 2) who have elected to undergo primary total knee arthroplasty performed at PeaceHealth Sacred Heart Medical Center at RiverBend or Slocum Ambulatory Surgery Center by [name], [name], [name] or [name]. Between 2005-2010, they performed a total 2,066 TKAs. Of those, 1,406 of the patients were between 50-80 years of age (68%). A total of 120 subjects will be enrolled in the two study aims.

- **Aim #1.** The biochemistry study aim will obtain complete data on **40 subjects**, randomized to either EAA supplementation or placebo, and further randomized to receive 1 week or 2 week post-surgical biopsies. Randomization is stratified by gender. Up to 70 subjects will be enrolled to account for withdrawal and attrition.

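### Mitochondrial respiration and fibre CSA are scored against a non-operative leg that the oral supplement also reaches, with no formula, so the score alone cannot answer EAA versus Placebo

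*Combined protocol and SAP*

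**What the plan says.** The scoring rule is in Study Aim #1, Primary Biochemical Outcome Measures: CSA and respiration "will be determined based on percent change from baseline and made relative to the non-operative leg (internal control". The Mitochondrial respiration paragraph repeats it for that outcome, proposing to measure respiration "using the Oroboros O2k respirometer, and normalize results statistically and use the non-operative leg as internal control". Potential Limitations, Statins, says the same and gives the reason: "Over 50% of our TKA subjects use statins". That paragraph also promises the analysis will proceed "while accounting for statin use between groups as well as between sex and over time statistically". No section says whether the relative score is a difference, a ratio, a quotient or a regression adjustment.

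The Secondary Physiological Outcome Measures of Aim #2 are defined by reference to the Aim #1 primary measures. Biopsies are bilateral at each biopsy time and, in Aim #2, optional.

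Data Analysis names ANCOVA for the research questions of both aims. It does not say whether the CSA or respiration outcome is the operative leg, each leg or the relative score. Its only sentence naming these two outcomes compares them with functional mobility.

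On where EAA acts:
- Investigational Supplement: "The investigational supplement (or Placebo) will be ingested twice-daily, at 10:00a and 2:00p for one week prior to TKA surgery". The treatment is oral, so it reaches both legs.
- Preliminary Studies, Biochemistry: "quadriceps atrophy was only -6% & -3% in the operative and non-operative quadriceps, respectively, six weeks after TKA but -18% & -10" percent in patients on Placebo.
- Preliminary Studies, Physiology: "Preventing muscle atrophy bilaterally is clinically important, as early post-operative quadriceps weakness in the non-operative leg is directly linked to poorer long-term functional outcomes".
- Effect sizes: d = 1.52 for operative and d = 1.05 for non-operative quadriceps volume.
- Potential Research Benefits: a 3-fold reduction in atrophy is claimed for both lower extremities.

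**The concern.** An internal control is useful when the treatment does not reach it. Here it does, and the protocol expects a response there. A score relative to that leg estimates how much more EAA does in the operative leg than in the other one. Questions 1.6 and 2.8 ask whether EAA changes markers of mitochondrial function versus Placebo, and the Hypothesis and the statement of Aim #2 set a general aim of better muscle-cell structure and function versus Placebo. Neither is limited to a contrast between legs. A real bilateral benefit could be reported as small or absent.

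The missing formula adds to this. The candidate readings give different estimates from the same data, and the choice could be made after results are seen.

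**Working it through.** The plan gives no effect size or power figure for the leg-relative score, so there is none to reproduce. The check applies each possible reading to the protocol's own per-leg figures. These are quadriceps volume at six weeks, used as a stand-in because no CSA or respiration results by leg and arm are given.

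**Inputs.** EAA: −6% operative, −3% non-operative. Placebo: −18% operative, −10% non-operative. d = 1.52 and 1.05. Two-sided alpha 0.05. 10 per group, the Aim #1 number for metabolic studies.

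**Effect in each leg (EAA minus Placebo).** Operative: −6 − (−18) = 12 points. Non-operative: −3 − (−10) = 7 points.

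**Reading 1, difference of percent changes.** EAA: −6 − (−3) = −3. Placebo: −18 − (−10) = −8. Gap: 5 points, so 7/12 = 58% of the operative-leg effect is gone. An effect equal in both legs gives exactly zero. If each whole-number input is off by up to 0.5, the gap is 3 to 7 points.

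**Reading 2, ratio of remaining volume.** EAA: 0.94/0.97 = 0.969. Placebo: 0.82/0.90 = 0.911. Gap: 5.8 points, 52% removed. With the same rounding, the gap is 3.7 to 7.9 points.

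**Reading 3, quotient of percent changes.** EAA: −6/−3 = 2.0. Placebo: −18/−10 = 1.8. EAA looks slightly worse although it lost less muscle in both legs. With rounding, the EAA value runs from 5.5/3.5 = 1.57 to 6.5/2.5 = 2.6 and the Placebo value from 17.5/10.5 = 1.67 to 18.5/9.5 = 1.95. The direction can reverse, but need not.

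**Reading 4, the other leg as a regression covariate.** Implied SDs: 12/1.52 = 7.89 and 7/1.05 = 6.67. With correlation ρ between legs, the slope is ρ × 7.89/6.67 = 1.184ρ, and the adjusted effect is 12 − 7 × 1.184ρ.

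**Power at 10 per group, ρ assumed.** For reading 1, SD = √(7.89² + 6.67² − 2ρ × 7.89 × 6.67) and d = 5/SD, with noncentral-t power. Reading 4 was simulated (20,000 runs per cell).

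| ρ (assumed) | Reading 1: SD | d | power | Reading 4: effect | removed | power |
|---|---|---|---|---|---|---|
| 0 | 10.33 | 0.48 | 18% | 12.0 | 0% | about 78% |
| 0.5 | 7.36 | 0.68 | 30% | 7.9 | 35% | about 55% |
| 0.8 | 4.75 | 1.05 | 61% | 5.4 | 55% | about 54% |
| 0.9 | 3.47 | 1.44 | 86% | 4.5 | 62% | about 66% |

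The operative leg analysed directly has d = 1.52 and 89% power. Under reading 1, d returns to 1.52 at ρ of about 0.91. Allowing for rounding of the inputs, reading 1 at ρ = 0.9 gives 48% to 94%, so the loss may be nil.

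**What the numbers rest on.** The published d values are covariate-adjusted, while the SDs above treat them as raw. ρ is not in the documents. Whole-muscle volume at six weeks also stands in for biopsy measures taken at one or two weeks in Aim #1.

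**The case against.** Several points on the other side stand.

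The between-leg comparison is intended. Preliminary Studies, Physiology, expects CSA in the EAA group to move towards the non-operative side, and the Aim #1 Randomization Assignments section plans a comparison between legs. No numbered question names CSA. For CSA the point is therefore weaker and rests on the general structural aim; the contrast should stay.

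An EAA versus Placebo comparison is planned. ANCOVA is to answer the research questions, and 1.6 and 2.8 are arm comparisons; only the leg is unspecified. Appendix 1 lists the bilateral biopsy as a source of study endpoints, the Muscle Morphology paragraph describes CSA without contralateral scoring, and nothing says that the relative score will be the only reported result. A reader might infer that no arm comparison exists. The documents do not support that. What they lack is a statement of which values enter it, and the only scoring rule they state is leg-relative.

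The internal control has a purpose. It removes a statin effect common to both legs. It also removes the common EAA effect, and the same paragraph already promises a statistical adjustment for statin use.

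A reader might also infer that more than half the effect, or most of the power, is lost. That is not established: the share removed depends on the formula and, under regression adjustment, on ρ. The proxy is a different endpoint, and the power loss may be nil. Nor does the point touch type I error, or extend to protein synthesis, Westerns or gene expression, for which no contralateral score is stated.

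That Aim #2 takes over the scoring rule along with the measures is a natural reading of the cross-reference, but an inference.

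**Conclusion.** The concern holds for mitochondrial respiration and, less strongly, for CSA. The plan names as control a leg that the treatment reaches and in which the protocol itself reports an EAA effect on muscle volume, and it does not define the score. A difference or ratio of legs cancels any effect equal in both, a quotient of percent changes can reverse direction, and regression adjustment removes an amount that depends on the correlation between legs. None of these alone answers questions 1.6 and 2.8 or the general structural aim versus Placebo.

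The size for CSA and respiration is unknown. The fall from 12 points to 5 or 5.8 illustrates the mechanism in another endpoint and is not an estimate for these two.

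The reach is modest: Aim #2 secondary outcomes in patients who opt into biopsies, whose number is not stated. The Aim #2 website text says that the first part of the study was completed in 2016, so any change to the Aim #1 analysis is post hoc. It should be fixed, but it does not threaten the Aim #2 primary outcomes.

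**What to change.** For respiration and CSA, state that EAA is compared with Placebo in each leg on that leg's own values. Either fit the planned ANCOVA leg by leg, or use one model with arm, leg, arm × leg and a subject random effect. In Aim #2, use the same leg's pre-operative biopsy as the covariate. Report the between-leg contrast separately, as the arm × leg result, with its formula written out. Enter statin use as a covariate instead of relying on contralateral normalisation.

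This changes wording only; both legs are already sampled. It has two costs. Each outcome gains one more result, whose place in the testing order must be stated. The statin term costs a little power, and more if the other covariates listed under Power analyses (sex, tourniquet time, age, body mass index and three intake variables) are also fitted in small groups.

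For Aim #2, settle the wording before unblinding if that has not yet occurred; the documents do not say. Label any Aim #1 reanalysis post hoc.
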